### Study Medication Accountability:

All study medication supplied for this study will be retained in the locked Research Pharmacy at the Children's Hospital of Alabama. The only persons with access to this room are the Research Pharmacists. Dispensing of the drug will occur only by the Research Pharmacist to authorized study personnel. A study medication inventory (dispensing records) for all medications dispensed will be kept in the Research Pharmacy and will be kept up to date. Used and unused study medication will be stored at the site or pharmacy throughout the study. The investigator/pharmacist will keep record of all drugs received, used, and returned.

At study end, all used and unused vials of Diamyd product and placebo must be returned to the central facility and subsequently to the supplier (Diamyd Medical), unless the supplier has approved other arrangements. Any destruction of the vials must be approved by Diamyd Medical and performed in accordance with the documented approved procedure from the supplier.

All research medications will be labeled with the following:

- Subjects name
- Date of dispensing
- Name of investigational drug
- Directions for use
- Prescribers name
- Lot # (if applicable)
- Expiration date (if applicable)
- Caution label for Investigational Use Only

### 5.8 Blinding and Code Breaking

Investigator site staff, persons performing assessments, and data analysts will remain blind to the identity of the treatment from the time of randomization until database lock, using the following methods. (1) randomization data are kept strictly confidential until the time of un-blinding and will not be accessible by anyone else involved in the study, with the exception of the independent, un-blinded pharmacist approving the randomization scheme and providing unblinded safety data to the DSMB per request. (2) the identity of treatment will be concealed by the use of matching placebo to the study drugs that are identical in packaging, labeling, and appearance and scheduled administration. Participants will be blinded in the same manner from randomization until their 12 month research visit. At that time, they will be un-blinded to their GABA treatment by the means of a sealed letter from the research pharmacist. This is done so that those who have received active GABA can continue their treatment, if they so choose, by purchasing GABA over the counter and not potentially losing beta cells as a result of discontinued therapy until results are available (2018/2019). It also allows those who have received placebo to not feel obligated to purchase GABA over the counter since we do not feel there would be benefit after 12 months of placebo therapy. The GAD status will remain blinded throughout the study for all participants. The participants and their families are asked to keep the letter in strictest confidence by not discussing with any study or clinic staff, and present or potential participants to the study.

The treatment code may be broken on an individual basis, in case of an SAE for which the investigator must know the study agent identity to initiate appropriate treatment. The investigator will be supplied the necessary information to break the study blind on an individual patient basis. If the code is broken for one individual subject, the date, time, and reason for un-blinding, together with the investigators signature, must be recorded and the sponsor and Diamyd, or its designee must be notified within 24 hours. Patients will continue in the study unless it is deemed inappropriate.

Suspected unexpected serious adverse reactions (SUSARS) will, if required, be un-blinded for reporting to regulatory agencies and ethics committees, Diamyd Medical, Janssen/JDRF (or its designees) will be supplied with the necessary information to break the study blind for individual patients as required for regulatory reporting purposes. However, the investigator, sponsor, and study team will be kept blinded to the treatment allocation.

The study blind will be broken when all patients have completed the study, and all data for this period has been entered into the database and locked. One randomization list is retained by the un-blinded pharmacist. After the database lock, the results will be analyzed and un-blinded where after a 12 month analysis will be performed.

## 6 Visit Schedule, Study Procedures, and Laboratory Measurements

6.1 Our new-onset type 1 diabetic children are admitted to the hospital, typically at most for two days, for initial glucose management and diabetes education. Diabetes is defined per ADA recommendation [20]. All patients with newly diagnosed type 1 diabetes return for follow up at approximately one month after diagnosis. Prior to this visit subjects may be enrolled if consented and enrollment criteria is met. This will serve as the baseline visit. The second visit should then be scheduled one month from the baseline visit (second injection with GAD-alum/placebo) with a visit window of +/- 7 days. Please note that all visits must be calculated from the baseline visit according to the visit schedule. See table 2 for schedule of patients visits, visit windows and study drug administration.

If patients are febrile when scheduled for an injection, treatment will be postponed until the patient is afebrile.

**Table 2 Schedule of Patient Visits, Visit Windows and Study Drug Administration**

Study	Intervention				
	Day 1 Baseline	Month 1	Month 5	Month 8	Month 12
	Visit 1	Visit 2 ± 7	Visit 3 ± 7	Visit 4 ± 7	Visit 5 ± 7
GABA/ Placebo	Every day from Day 1 through Month 12				
GAD-alum/ Placebo	Prime: One injection	Boost: One injection			

### 6.2 Study Events

The treatment therapy consists of oral GABA or placebo given with meals twice daily at breakfast and dinner throughout the study and 2 GAD-alum or placebo injections given at baseline and 1 month later . i.e.1 prime and 1 booster dose.

Study visits for all patients will occur for randomization at baseline and subsequently for the injection, and for medical monitoring.

General assessments include:

- medical history and routine physical exam
- concomitant medications
- adverse events
- Laboratory Assessments (hematology, biochemistry, urine pregnancy test as appropriate, islet antibodies, liver function and urine studies)

Metabolic assessments include:

- Glucose records and reports of hypoglycemia
- Insulin Dose
- HbA1c
- Mixed Meal Tolerance Test

#### 6.2.1 Mixed Meal Tolerance Test

Participants will undergo a mixed meal tolerance test at their outpatient visits as outlined in the instructions below.

- On the evening before the MMTT, subjects will eat a full, standard meal. They will be asked to fast from 9 pm the evening before the test until the MMTT is completed. They should remain hydrated and may consume water during the fast and test.
- Subjects will be instructed to take their long acting insulin the night before the test, but not to administer short-acting insulin for at least 6 hours before the morning MMTT test.

- Participants must have a fasting plasma glucose level in the range of 72-216 mg/dL on the patient's home glucose monitoring device the morning of the test. If for safety reasons, subjects need to eat or take insulin, the visit will need to be rescheduled.
- An Intravenous catheter will be inserted just prior to the test and then GABA or placebo will be given just prior to drinking the Boost High Protein drink (1 cal/mL; 55% carbohydrates, 21% lipids and 24% protein). They will drink 6 ml/kg Boost, up to maximum of 360 ml, to be ingested within 5 minutes. Blood samples from an intravenous catheter are collected 10 minutes prior to the meal (-10), at the time of ingestion (0), and at 15, 30, 60, 90 and 120 minutes thereafter. This schedule will be followed at the baseline and 12 month visits. At 1 month and 5 month visits only a fasting and 90 min sample will be taken. There will not be a MMTT on month 8.
- 3 cc's of urine (if available) will be placed in an aliquot tube and frozen for evaluation of urine C-peptide. The remaining sample will be used for evaluation of microalbuminuria and creatinine levels.

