Study Design: The study is a 3-arm, randomized, double-blind, placebo-controlled, clinical trial. Patients will receive either 
 
i) oral GABA, dosed per kg, twice daily for 12 months plus 2 subcutaneous injections of 20 µg Diamyd in a prime-and-boost regimen over a period of 30 days
 
ii) oral GABA, dosed per kg, twice daily for 12 months, Placebo GAD-alum 2 subcutaneous injections over a period of 30 days.
 
iii) placebo.
 
 
The patients will be followed for a total of 12 months.

Selection of Subjects: Patients must be age 4 to 18years old, and diagnosed with Type 1 Diabetes (T1D) within the previous 5 weeks of randomization. Patients must be positive for GAD-65 autoantibody to be enrolled. They may, or may not be positive for the other autoantibodies at the time of enrollment, but all will be followed during the study.
Number of Subjects Planned: Approximately 110 patients will be enrolled.
Description of Treatment Groups: The patients will be assessed for eligibility prior to randomization. On Visit 1 (Day 1, baseline), patients eligible for the study will be randomized to 1 of 3 treatment groups: 
 
• 30 patients will be assigned to receive oral GABA twice daily, dosed per kg, from Day 1 through Month 12. In addition 2 subcutaneous injections with 20 µg Diamyd (GAD-alum) will be given at Day 1 and Month 1, i.e., 1 prime and 1 booster dose (providing a total dose of 40 µg Diamyd).
 
• 43 patients will be assigned to receive oral GABA twice daily, dosed per kg, from Day 1 through Month 12. In addition 2 subcutaneous injections with Placebo GAD-alum will be given at Day 1 and Month 1
 
• 37 patients will be assigned to receive oral Placebo GABA twice daily, dosed per kg, from Day 1 through Month 12. In addition 2 subcutaneous injection with Placebo GAD-alum will be given at Day 1 and Month 1
 

Name of Sponsor [name]
Name of Finished Product: GABA (Gamma-Aminobutyric Acid) DIAMYD® 20µg, subcutaneous injection (GAD-alum)
Name of Active Ingredient: Gamma-Aminobutyric Acid (GABA) Recombinant Human Glutamic Acid Decarboxylase (rhGAD65)

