
Primary Endpoint:
 
 
Evaluate the effect of GABA and GABA + GAD-alum combination on pancreatic beta cell function, as measured by meal stimulated C-peptide secretion levels compared to age-matched placebo controls, before and after one year of treatment.
 
 
Secondary Endpoints:
 
 
Evaluate the effect of GABA and GABA + GAD-alum combination on autoimmune diabetes autoantibodies: GAD-65, ICA512, and Zinc Transporter 8(ZnT8A) and the effect on HbA1c, fasting and stimulated glucose & glucagon levels, fasting C-peptide and the amount of daily insulin usage by participants, from baseline through subsequent visits
 
Evaluate the safety of GABA and GABA/GAD-alum combination
 
 
Safety The safety assessment includes observation of reactions at the injection site, occurrence of adverse events (AEs), laboratory measurements, neurological assessments, and limited physical examinations.
 
Sample size: The sample size for the proposed study is 110 children; 30 in the treatment group of active GABA and active GAD-alum, 43 in the treatment group receiving active GABA and placebo GAD-alum, and 37 in the placebo group. For the primary comparison of the 12-month post-baseline C-peptide measurements between these groups, assuming an <math>\alpha</math> of 0.05 and a mean (SD) C-peptide AUC of 1.0 (0.4) this sample size yields a ~97% power to detect a 50% difference. Adverse events and other data will be summarized descriptively.

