**Table 3. Schedule of Study Events**

	At Baseline	1mo post baseline (+/- 1 week)	5mo post baseline (+/- 1 week)	8mo post baseline (+/-1 week)	12mo postbaseline (+/- 1week)
Informed Consent	X (or before)				
Randomization	X				
Gad-alum or placebo injection a	X	X			
Oral GABA or placebo administration starts	X				
Medical History	X				

Vital Signs	X	X	X	X	X
Ht	X	X	X	X	X
Weight	X	X	X	X	X
Physical Exam + Neurological	X	X	X	X	X
Hgb A1C	Done as standard of care at every visit.		Obtain results from chart		
Growth Rate	X	X	X	X	X
Hx of DKA	X	X	X	X	X
Autoimmune antibodies	Done as standard of care at diagnosis. Obtain and document results.		X		X
Mixed Meal Tolerance Test ( glucose, glucagon, C peptide, )	X	X (only fasting and 90 min samples)	X (only fasting and 90 min samples)		X
CBC with diff	X		X		X
Hx of Hypoglycemia	X	X	X	X	X
Complete Metabolic Profile	X		X		X
Glucagon( fasting), glucose, C-peptide	X	X	X		X
Urine Pregnancy test (for menstruating females)	X	X	X	X	X
Total Daily Insulin Dose( U/kg)	X	X	X	X	X
Medication Review/ Concomitant Medications	X	X	X	X	X
Cell Activation Markers	X		X		X
Inflammatory Cytokines	X		X		X
Skin exam: injection site: b	X	X	Ask regarding any issues after last injection. X		
Urinalysis (if available) for microalbuminuria and creatinine and C-peptide	X	X	X	X	X
Adverse Events	X	X	X	X	X
Proinsulin	X		X		X

a GAD-alum/Placebo administration: The target date for the second GAD-alum/Placebo administration will be set in accordance with baseline (i.e. the first injection, Visit 1) so that the second dose will be 1 month post first dose.

b Inspection of injection site before and 60 minutes after injection by investigator or nurse

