#### 6.7 Data Collection and Assays:

Subject visits will consist of a baseline visit and subsequent visits as noted above. The data noted in the table above will be collected by study personnel and stored in a locked office and on a password-protected UAB computer. All laboratory specimens will be collected by study personnel, labeled with the study participant's unique identifier and date of collection, and then stored at -80°C in [name] lab. Analysis of all laboratory measurements will be completed at the conclusion of the study.

- 1.) *Hemoglobin A1C*: Measured by latex immunoagglutination inhibition methodology( DCA 2000, Siemens-Bayer)
- 2.) *Mixed Meal Tolerance Test*: After an overnight fast, the patients will have an IV placed and will drink Boost. They will have C-peptide and glucose and glucagon levels drawn at 10 minutes prior to dose (-10), 0, 15, 30, 60, 90, and 120 min. The C-peptide, glucagon, and glucose levels will be assayed by the UAB Metabolism Core of the Clinical Nutrition Research Center (CNRC). At the 1 and 5 month visits, only a fasting and 90 minute sample are obtained. A recent 2013 article confirms that this 90- minute sample alone correlates significantly with the integral of the C- peptide as a function of time curve, oft-called the AUC [21].
- 3.) *Pancreatic Antibodies*: GAD-65, ICA512 and Anti-Zinc Transporter 8 samples are collected as standard of care at initial diagnosis. We will use these results as our baseline. Follow-up samples will be collected at the visits noted in the Table. Samples will be assayed at ESOTERIX Laboratory Services, Inc..
- 4.) *CBC with manual differentiation*: Performed at baseline and at the visits noted in the Table, and assayed in the hematology lab of Children's Hospital Alabama

- 5.) *Complete Metabolic Profile*: CMP will be monitored at the visits noted in the Table, and assayed in the chemistry lab of Children's Hospital Alabama.
- 6.) *Glucagon*: Glucagon levels will be measured under fasting conditions at the visits noted in the Table, and during the Mixed Meal Tolerance Tests. Assays will be conducted by UAB Metabolism Core of the Clinical Nutrition Research Center (CNRC).
- 7.) *Height*: Collected at each visit
- 8.) *Weight*: Collected at each visit to make dosing adjustments in the GABA .
- 9.) *Medications*: We will review total daily insulin dose and compliance. We will review all other non-study medications which the patients are taking.

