## 7.0 Adverse Event Reporting and Safety Monitoring

### 7.1 Adverse Events:

An adverse event (AE) is any untoward medical occurrence in a patient or clinical investigation subject administered a pharmaceutical product, and which does not necessarily have to have a causal relationship with this treatment. An AE can therefore be any unfavorable and unintended sign (including an abnormal laboratory finding, for example), symptom, or disease temporally associated with the use of a medicinal product, whether or not considered related to the medicinal product.

All treatment emergent AEs will be recorded from the baseline visit forward (First dose of study drug) for the duration of the study on source documents (i.e., original documents, data, and records). AEs include those reported spontaneously by the subject and those noted incidentally or as observed by the investigator or study personnel. To avoid vague, ambiguous, or colloquial expressions, the AE will be recorded using standard medical terminology that is as specific as possible, rather than the subject's own words. Whenever the investigator is confident in making a unifying diagnosis, all related signs, symptoms, and abnormal test results should be grouped together and recorded as a single AE (e.g., cough and rhinitis should be reported as an "upper respiratory tract infection").

All clinically significant abnormalities noted upon physical examination, or other diagnostic test results should be reported as an AE, except for baseline measurements that may be considered part of the medical history. In addition, all clinically significant AEs that continue at Study Termination should be followed up by the investigator and evaluated with additional tests if necessary, until the underlying cause is diagnosed or resolved, or is determined to have resolved without sequelae. All AEs will be evaluated for intensity and causal relationship with use of the study medication (or study procedures if applicable) by the investigator.

AEs that occur following completion of study termination/early termination procedures will be recorded on the AE page of the source documents only if the investigator considers the event as clinically significant and as related to study medication or study procedures. All adverse events that are deemed to be serious and meet the definitions provided in section 7.2, for serious adverse events will be reported as "SAE's."

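### Followed literally, Section 6.2.1 gives the first randomised GABA or placebo dose before the baseline meal test, so the stimulated baseline values are not pre-treatment

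*Combined protocol and SAP*

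**What the plan says.** Section 6.2.1 sets out one set of instructions for the meal tests at outpatient visits. Once the catheter is in, "GABA or placebo will be given just prior to drinking the Boost High Protein drink". Samples are due at -10, 0, 15, 30, 60, 90 and 120 minutes around the drink, and this schedule is assigned to baseline and month 12. The stated differences between visits concern sampling: "At 1 month and 5 month visits only a fasting and 90 min sample will be taken", and month 8 has no test.

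The other passages put the start of treatment at the same visit:

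- Synopsis, Description of Treatment Groups: "On Visit 1 (Day 1, baseline), patients eligible for the study will be randomized".
- Table 3 marks randomisation, the meal test and the row "Oral GABA or placebo administration starts" in the baseline column, without an order.
- Section 7.1 records adverse events "from the baseline visit forward (First dose of study drug", which equates the baseline visit with the first dose.
- Section 6.7 describes the test again ("the patients will have an IV placed and will drink Boost") without mentioning study drug. It times the -10 minute sample against a dose that it does not identify.

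The Synopsis and Section 4.2 define the primary endpoint as meal-stimulated C-peptide "before and after one year of treatment". Section 9 takes the month-12 value as the dependent variable and adjusts for baseline C-peptide.

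**The concern.** A baseline covariate is safe in ANCOVA because randomised treatment cannot have touched it. If a child takes the assigned capsules and then has the baseline test, the stimulated part of that baseline is an outcome of treatment. Any acute effect of one dose is then partly subtracted from the 12-month comparison.

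The two active-versus-placebo contrasts are exposed. GABA/GAD-alum versus GABA is largely spared, because both arms take GABA. Stimulated glucagon, a secondary outcome, is where an acute effect is most plausible: Section 3 says that GABA acts on alpha-cells and suppresses glucagon. For C-peptide, the primary outcome, the documents describe no acute effect.

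**Working it through.** **1. Order of steps.** Section 6.2.1 puts the capsule before the drink, and the 15 to 120 minute samples follow the drink. They therefore follow the capsule at any visit where the instruction is carried out. Baseline is a meal-test visit, it is the visit of randomisation and first dose, and it is not exempted. The -10 minute sample is apparently pre-dose. Whether the 0 minute sample precedes the capsule is not stated.

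**2. Formula.** Let L be the long-term effect, d0 and d12 the acute shifts at baseline and month 12, rho the baseline-to-month-12 slope, and f the share of active-arm baselines that were dosed. The expected ANCOVA contrast is L + d12 - rho × f × d0.

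- On-drug target (L + d12): error = -rho × f × d0.
- Long-term-function target (L): error = d12 - rho × f × d0.

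With d0 = d12 = 0, both errors are zero.

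**3. Inputs.** From the documents: SD 0.4, mean AUC 1.0 and a 50% difference, hence a planning difference of 0.5 (Section 10); 43 GABA, 30 GABA/GAD-alum and 37 placebo (Section 5.6). Assumed, because the documents give neither: d0, d12 and rho.

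**4. C-peptide, on-drug target.** With d0 = 0.1, f = 1 and rho = 0.5 / 0.7 / 0.8:

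- error = -0.05 / -0.07 / -0.08, i.e. 10 / 14 / 16% of 0.5;
- a shift of -0.1 reverses the sign.

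**5. C-peptide, long-term-function target, GABA versus placebo.** With an acute shift of 0.1 at each dosed test and no long-term effect:

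| Tests dosed | Error at rho 0.5 / 0.7 / 0.8 | Simulated false-positive rate |
|---|---|---|
| Baseline and month 12 | 0.05 / 0.03 / 0.02 | about 6 to 9% |
| Month 12 only | 0.10 / 0.10 / 0.10 | 24 / 34 / 45% |

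Under this target the error comes from the month-12 dose, and the dosed baseline cancels part of it (0.10 - 0.7 × 0.10 = 0.03).

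**6. Stimulated glucagon, illustration only.** Assume the Section 9 ANCOVA, an on-drug target, and the same shift at both tests with L = 0. The share of the effect kept is 1 - rho: 50 / 30 / 20%. For a shift of -0.5 SD, 43 versus 37, simulated power is 72 / 87 / 95% with a pre-dose baseline and 23 / 14 / 11% with a dosed one.

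**7. The -10 minute value as covariate.** The standard-error ratio is sqrt(1 - r²) / sqrt(1 - rho²), where r is its correlation with the month-12 outcome. With rho = 0.7, the denominator is sqrt(0.51) = 0.714. For r = 0.4 / 0.5 / 0.6 the numerators are 0.917 / 0.866 / 0.800, giving ratios of 1.28 / 1.21 / 1.12.

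**The case against.** The dosing sentence may simply describe the breakfast dose of patients already on drug. The sentence applying the schedule to baseline and month 12 follows the list of sampling times, so it may cover sampling alone. A first dose taken after the test, or at dinner, would still start treatment on Day 1, and the endpoint wording favours a pre-treatment baseline. This reading is fair. It turns the contradiction into an ambiguity, but the order that fixes the primary covariate is still unwritten, and the unidentified dose in Section 6.7 does not supply it.

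A dosed baseline matched to a dosed month 12 could also be deliberate like-for-like testing. The documents do not say so, and such a baseline would still not be a before-treatment value.

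Three stronger inferences are tempting, and the documents support none of them.

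- A reader might take the 6 to 9% false-positive rates in step 5 as harm from the dosed baseline. They arise from the month-12 dose.
- A reader might conclude that the primary result is biased. That needs an acute C-peptide effect, which the documents do not report. Much higher rejection rates, such as about 80% with slope 0.8 and shift 0.2, also require that month 12 carries no acute effect, although Table 2 continues the drug through month 12.
- A reader might treat the glucagon power loss as a finding. Section 3 gives a mechanism without size or time course, and Section 9 does not clearly say that glucagon gets the ANCOVA.

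**Conclusion.** The point holds as a conflict within the protocol about when the stimulated baseline is measured. On the literal reading, the baseline is post-dose and the Section 9 covariate can be affected by treatment. On the milder reading, the order is undefined and the same passages still need reconciling. The fasting (-10 minute) baseline is probably unaffected.

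The statistical consequence is conditional. Its form against an on-drug target is known (step 2), but its size and sign are not, and it may be zero. The figures in steps 4 to 6 show scale under assumed shifts and slopes; they are not estimates for this trial. The textual defect is clear and cheap to correct, so the change should be made even though the harm cannot be quantified.

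**What to change.** 1. Reconcile Section 6.2.1, Table 3 and Section 6.7 with the primary endpoint (Synopsis, Section 4.2) and Section 9, so that the baseline meal-test samples used in the analysis precede the first randomised oral dose.
2. In the same revision, settle the study-drug condition of the month-12 test and state whether its value estimates on-drug response or preserved function. Changing baseline alone leaves the whole of d12 in the contrast, which matters if preserved function is the target.
3. Section 6.7 refers to participants who have already completed visits. For baselines already done, establish the order of dose and samples from existing records where possible, and report the number of dosed baselines by arm.
4. If any baseline followed dosing, add one sensitivity ANCOVA for all patients with the -10 minute C-peptide as covariate. Do the same for stimulated glucagon with its -10 minute value, once its model is stated.

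The cost is a few lines on order in Section 6.2.1 and Table 3 and a short paragraph in Section 9. No visit or blood sample is added, because the -10 minute sample is already drawn.

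There are limits. The order at past visits is lost if it was not recorded. A mid-trial change mixes dosed and undosed baselines: with d0 = 0.1, rho 0.7 and 25 to 75% dosed, the on-drug error is about -0.02 to -0.05. The sensitivity analysis has a standard error about 12 to 28% larger under the assumed correlations, and it does not remove a month-12 acute effect.
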